5.1 Statistical Methods

5.1.1 Hypotheses and Statistical Methods for Primary Objective(s)

There are no primary objectives in this trial.

5.1.2 Hypotheses and Statistical Methods for Secondary Objective(s)

There are no secondary objectives in this trial.

5.1.3 Statistical Methods for Observational Objective(s)

5.1.3.1 Hypothesis

No hypotheses will be tested. Descriptive statistics will be presented.

5.1.3.2 Statistical Methods

5.1.3.2.1 Demographics and disposition

Summaries of the recruitment and baseline demographic characteristics of the study subjects will be presented. The number of subjects enrolled and their age at enrollment (mean, median, and minimum and maximum), sex, and ethnic origin will be summarized, along with the number and description of protocol violations.

5.1.3.2.2 Safety

The number and percentage of subjects reporting any solicited injection site reactions and solicited systemic reactions will be summarized by study group, intensity (Grade 1, Grade 2, and Grade 3), and period (D0 to D3, D4 to D7, and D0 to D7 after vaccination) for each reaction term. For a time period in which more than 1 intensity was recorded, the highest intensity will be used. Exact (Clopper-Pearson) 2-sided 95% confidence intervals (CIs) will be calculated for the percentages.

Immediate reactions, unsolicited AEs (including MAAEs), and SAEs will be coded and presented by MedDRA preferred term and system organ class (SOC). The number and percentage of subjects reporting safety findings will be summarized by study group for each preferred term, and SOC that has at least 1 report, as well as by relationship to study vaccine. SAEs will be tabulated separately from D0 through the end of the 6 month follow-up. Unsolicited AEs representing a change in the health status of the subject will be presented from D0 through D30. MAAEs will be presented from V01 through V02 through the end of the 6-month follow-up period.

Descriptive statistics will include, but not be limited to:

Table 5.1: Statistical analyses for safety observational objective

Safety Events	Time and Group	Description
Immediate unsolicited systemic AE	Within 30 minutes after injection for all subjects in Groups 1 - 6 at D0	Percentage of subjects that have the event, MedDRA terms, intensity, relationship to vaccine, study discontinuation, duration
Extensive limb swelling	Up to 7 days after D0 for all subjects in Groups 1 – 6	Percentage of subjects that have the event
Solicited injection site reactions	Up to 7 days after D0 for all subjects in Groups 1 – 6	Percentage of subjects that have the event, time of onset, duration, intensity, action taken, study discontinuation, number of days of occurrence
Solicited systemic reactions	Up to 7 days after D0 for all subjects in Groups 1 – 6	
Unsolicited AE	Up to 7 days after D0 for all subjects in Groups 1 – 6 From D0 to D30 for all subjects in Groups 1 – 6	Percentage of subjects that have the event, MedDRA terms, time of onset, duration, intensity, relationship, action taken, study discontinuation
SAE	Up to 7 days after D0 for all subjects in Groups 1 – 6 From D0 to D30 for all subjects in Groups 1 – 6 From D31 to 6-month follow-up contact for all subjects in Groups 1 – 6 Up to 6-month follow-up contact after D0 for all subjects in Groups 1 – 6	Percentage of subjects that have the event, MedDRA terms, time of onset, duration, relationship, seriousness criteria, outcome, study discontinuation
MAAE	From V01 to V02 for all subjects in Groups 1 - 6 (as unsolicited AE) From V02 to 6-month follow-up contact for all subjects in Groups 1 - 6	Percentage of subjects that have the event, MedDRA terms, time of onset, duration, intensity, relationship, action taken, outcome, study discontinuation

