	
The following safety parameters will be assessed as part of the early safety review and the continuous safety analyses:
 
 
• Immediate unsolicited AEs
 
• Solicited injection site and systemic reactions
 
• Unsolicited AEs
 
• SAEs
 
• MAAEs
 
 
Enrollment will be paused during the ESDR, and the data will be examined for the following alert thresholds defined for this study:
 
 
• Extensive limb swelling (ELS) among <math>\geq 3\%</math> recipients of any of the investigational formulations
 
• Any life-threatening event or death considered related to vaccination by the Investigator among recipients of any of the investigational formulations
 
 
If any of the above criteria are met during the per-group partially-blinded safety review, a decision will be made as to whether enrollment of the affected group in the study will be allowed to continue. Only in case of further concern, complete unblinding and further in-depth review of safety data will be conducted. Continuation will be determined pending final results of the early safety review. If the risk for certain formulation(s) has been determined as high, enrollment of the next age groups (adolescents and older adults) for the respective formulation will not proceed.
 
The usual and ongoing process of monitoring safety signals outside of those specified in the protocol-defined early interim safety analysis will continue unchanged.
 
Apart from the ESDR and the ongoing safety review, the study may be interrupted at any time if new data about the investigational product become available, and/or on advice of the Sponsor, the Institutional Ethics Committees (IEC)/Institutional Review Boards (IRB), or the governing regulatory authorities in the US where the study is taking place.
 
If the study is prematurely terminated or suspended, the Sponsor will promptly inform the Investigators, the IECs/IRBs, and the regulatory authorities of the reason for termination or suspension. If the study is prematurely terminated for any reason, the Investigator will promptly inform the study subjects / subjects' parents/guardians and should assure appropriate therapy and follow-up.

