
Planned Sample Size:
	
A total of 1350 subjects are planned to be enrolled and randomized to 1 of 6 study groups. Within each group subjects will be stratified by age in a 1:1:1 ratio as shown below.
 
Table S2: Randomization by study group.
 
  
 Study group	Vaccine formulation	Pertussis Adjuvant	Subjects, N	
 
 10–18 years	19–64 years	≥ 65 years	
   
 1	SP0173-low	██████	75	75	75	
 
 2	SP0173-middle	██████	75	75	75	
 
 3	SP0173-middle	██████	75	75	75	
 
 4	SP0173-high	██████	75	75	75	
 
 5	Adacel® control	██████	75	75	75	
 
 6	BOOSTRIX® control	██████	75	75	75	
  
	Study group	Vaccine formulation	Pertussis Adjuvant	Subjects, N			10–18 years	19–64 years	≥ 65 years	1	SP0173-low	██████	75	75	75	2	SP0173-middle	██████	75	75	75	3	SP0173-middle	██████	75	75	75	4	SP0173-high	██████	75	75	75	5	Adacel ® control	██████	75	75	75	6	BOOSTRIX ® control	██████	75	75	75
Study group	Vaccine formulation				Pertussis Adjuvant	Subjects, N																																								
		10–18 years	19–64 years	≥ 65 years																																										
1	SP0173-low	██████	75	75	75																																									
2	SP0173-middle	██████	75	75	75																																									
3	SP0173-middle	██████	75	75	75																																									
4	SP0173-high	██████	75	75	75																																									
5	Adacel ® control	██████	75	75	75																																									
6	BOOSTRIX ® control	██████	75	75	75																																									

Schedule of Study Procedures:	
Vaccination
 
All subjects will be randomized to receive 1 dose of an SP0173 formulation, Adacel®, or BOOSTRIX®.

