## 3 Investigators and Trial Organization

This study will be conducted in approximately 20 centers in the US. Details of the study centers and the Investigators at each center are provided in the “List of Investigators and Centers Involved in the Trial” document.

The safety of the investigational product will be continuously monitored by the Sponsor and will include 3 types of surveillance:

- *Ongoing safety surveillance* of SAE.
- *Periodic safety surveillance* (during enrollment and safety data collection for each of the 2 sets of age cohorts: adults followed by adolescents/older adults) [REDACTED]
- *Early Safety data review (ESDR)*, during which enrollment in the study (between age cohorts) will be paused. [REDACTED]

Immunogenicity testing will all be performed at the Sanofi Pasteur Global Clinical Immunogenicity (GCI) laboratories in Swiftwater, PA, USA.

The Sponsor's Responsible Medical Officer (the person authorized to sign this protocol and any amendments on behalf of the Sponsor) is [REDACTED], [REDACTED], Clinical Team Leader (CTL) or such delegate as may be identified in her absence.

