## 6.5 Randomization and Allocation Procedures

The Sponsor or designee will supply a centralized, age- and site-stratified, computer-generated randomization code. The computer-generated randomization code will assign subjects to 1 of 6 groups.

Each subject who meets the eligibility criteria and signs an informed consent form will be randomly assigned to 1 of 6 groups via an IVRS/IWRS Site. Unblinded site staff will call the IVRS/IWRS, enter identification and security information, and confirm a minimal amount of data in response to IVRS/IWRS prompts. The IVRS/IWRS will then state the subject number and the group subset, and have the caller confirm this. Subject numbers will be recorded on the eCRFs. The full detailed procedures for randomization are described in the OG.

Subject numbers will be 8 digits long, with a 3-digit center identifier and a 5-digit subject identifier. For example, Subject 001-00001 is the first subject enrolled in center number 1.

Subject numbers should not be reassigned for any reason.

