## 12.1.2 Statistical Methods for Observational Objectives

### Safety/Reactogenicity

The number and percentage of subjects reporting any solicited injection site reactions and solicited systemic reactions will be summarized by study group, intensity (Grade 1, Grade 2, and Grade 3), and period (Days 0 to 3, Days 4 to 7, and Days 0 to 7 after vaccination) for each reaction term. For a time period in which more than 1 intensity was recorded, the highest intensity will be used. Exact (Clopper-Pearson) 2-sided 95% confidence intervals (CIs) will be calculated for the percentages.

Immediate reactions, unsolicited AEs (including MAAEs), and SAEs will be coded and presented by MedDRA preferred term and SOC. The number and percentage of subjects reporting safety findings will be summarized by study group for each preferred term, and SOC that has at least 1 report, as well as by relationship to study vaccine. SAEs will be tabulated separately from D0 through the end of the 6-month follow-up. Unsolicited AEs representing a change in the health status of the subject will be presented from D0 through D30. MAAEs will be presented from V01 through V02 and from V02 through the end of the 6-month follow-up period.

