5.4 Interim / Preliminary Analysis

No interim analyses are planned. An initial internal safety review (ESDR) for this study is planned when all adult subjects have been vaccinated and have provided safety data for V01 through V02 post-vaccination, using the data collection methods described in the protocol. The safety data collected will be entered into the electronic case report forms (eCRFs), and will be summarized and reviewed in a per-group partially blinded (group unblinded) fashion by the Sponsor. It is understood that this review will be based on preliminary data that have not been subject to validation and database lock. No statistical adjustment is necessary because no hypotheses will be tested.

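### Final safety tables are specified by vaccine group only; no final safety summary is pre-specified for the three randomised age strata

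*SAP*

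**What the plan says.** **How safety is summarised.** For solicited reactions, SAP 5.1.3.2.2 states that "solicited systemic reactions will be summarized by study group, intensity (Grade 1, Grade 2, and Grade 3), and period". For unsolicited events, SAEs and MAAEs, Protocol 12.1.2 states: "The number and percentage of subjects reporting safety findings will be summarized by study group for each preferred term". The Protocol synopsis and SAP 5.1.3.2.2 carry the same rule. SAP Table 5.1 lists its rows for all subjects in Groups 1 to 6 and has no age row or column.

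**What a study group is.** The synopsis defines six study groups, one per vaccine or formulation, and says: "Within each group subjects will be stratified by age in a 1:1:1 ratio". Table S2 there gives 75, 75 and 75 subjects aged 10–18, 19–64 and ≥ 65 years. Protocol 6.1 uses Groups 1–4, 5 and 6 in the same sense.

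**How age is treated elsewhere.** Protocol 6.5 specifies a "centralized, age- and site-stratified, computer-generated randomization code". The immunogenicity text in SAP 5.1.3.2.3 is split by age. SAP 5.1.4 allows optional output for ages 65–74 and ≥ 75.

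**The concern.** The trial is meant to select a formulation for people aged 10 and over, and describing each formulation's safety is one of its two objectives. The design itself treats age as relevant to safety: under the step-down, adolescents and older adults are enrolled only after the adult data have been reviewed. Yet the final plan promises no separate safety summary for those two strata.

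A reaction concentrated in one stratum would be averaged with two strata where it is rare. A reassuring all-age figure could then be taken as evidence about adolescents or older adults that it does not supply.

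If 1:1:1 enrolment is completed in every group, the vaccine groups have the same age mix, so the problem is dilution and not bias between arms. That protection depends on complete enrolment. The synopsis and the Protocol's early safety review text allow a formulation judged high-risk not to proceed to the later age groups. An all-age column for that formulation would then hold adults only, beside columns that span all ages.

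**Working it through.** **1. The plan's own figures (Protocol 12.5, SAP 5.5).** The probability of seeing at least one event is 1 − (1 − p)^N.

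| N | Incidence p | Computed | Stated |
|---|---|---|---|
| 1350 | 0.2% | 93.3% | about 93% |
| 225 | 1.3% | 94.7% | about 95% |
| 225 | 0.2% | 36.3% | about 36% |

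All three reproduce, and N = 225 per formulation is the number pooled over age (3 × 75). The stated 67 evaluable subjects per group fits 75 × 0.9 = 67.5 and not 225 × 0.9 = 202.5, so that figure refers to one vaccine-by-age cell.

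**2. What zero events would show.** The method is the plan's own: exact (Clopper-Pearson), two-sided 95%. With zero events the upper limit is 1 − 0.025^(1/n).

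- All-age column, n = 225: 1.6%.
- One age stratum, n = 75: 4.8%.

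These use planned sizes and assume no event rate.

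**3. Dilution.** With equal strata the all-age rate is (r₁ + r₂ + r₃)/3. If events occur in one stratum only, the reported rate is one third of the true stratum rate (225/75 = 3). This is the maximum.

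The event counts below are assumptions; all events fall in one stratum and none in the other 150 subjects.

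| Events | In the stratum (n = 75) | All-age column (n = 225) |
|---|---|---|
| 3 | 4.0% (0.8–11.3%) | 1.3% (0.3–3.8%) |
| 6 | 8.0% (3.0–16.6%) | 2.7% (1.0–5.7%) |

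If the reaction also occurs elsewhere, dilution is smaller. Assumed rates of 6%, 1% and 1% give (6 + 1 + 1)/3 = 2.7%, a factor of 6/2.67 = 2.25.

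**4. What is lost in single cells.**

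| | n = 75 | n = 225 |
|---|---|---|
| Probability of seeing an AE with 1.3% incidence | 62.5% | 94.7% |
| Incidence seen with 95% probability, 1 − 0.05^(1/n) | 3.9% | 1.3% |

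At 67 subjects the cell figures become 58.4% and 4.4%.

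**5. Provisions that might already fill the gap.**

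- *Early safety data review.* SAP 5.4: "An initial internal safety review (ESDR) for this study is planned when all adult subjects have been vaccinated". It covers adults only, from V01 to V02, is internal, and uses "preliminary data that have not been subject to validation and database lock".
- *Continuous safety analyses.* The synopsis introduces a list of parameters with "The following safety parameters will be assessed as part of the early safety review and the continuous safety analyses". This sets what is monitored during the trial and defines no final table.
- *Periodic surveillance.* Protocol 3 places it "during enrollment and safety data collection for each of the 2 sets of age cohorts". This is also monitoring, and it treats adolescents and older adults as one set.
- *Open list.* The SAP says its descriptive statistics are not confined to those listed. That permits age tables without committing to them.
- *SAP 5.1.4.* The 65–74 and ≥ 75 output is optional, names no endpoint and does not follow the randomised strata. It may presuppose an analysis of those ≥ 65, but does not specify one.

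**The case against.** The strongest reply is that the plan leaves the age split unstated and does not choose pooling. Three things support this.

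- The sample-size text uses *group* for the 75-subject cell, so the authors may have had vaccine-by-age tables in mind.
- The prose does not list every table dimension. The demographics text names no arm-level split either, and nobody would infer demographics without arms.
- SAP Table 5.1's reference to all subjects in Groups 1 to 6 does not prove pooling, because SAP Table 5.2 uses the same words for immunogenicity, which is analysed by age.

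The intention may well have been to tabulate by age. But the safety sections do state a rule, by study group, and Table S2 defines that term as a vaccine across all ages. The immunogenicity prose adds an age split and the safety prose does not. Some tables and early-review text are redacted, but the final safety-analysis sections are intact.

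It can also be said that the consequence is limited: no hypotheses are tested, no final decision rule uses the all-age rate, and age tables can be produced at any time from data already collected. This is correct, and it makes the point inexpensive to settle. It does not make later, optional tables equivalent to pre-specified ones.

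Last, the plan sizes detection of rarer events on 225 per formulation, and splitting every row gives 18 sparse cells (6 vaccines × 3 strata). That stands, and it is why the all-age column should be kept. The case for splitting is strongest for solicited reactions and extensive limb swelling.

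**Conclusion.** The concern holds. Followed literally, the plan yields one all-age safety rate per vaccine and pre-specifies no final safety output by the randomised age strata. It is a weakness in the analysis specification that should be corrected. It is not an error in any stated figure.

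The size is at most a three-fold dilution of a stratum-specific rate, reached only if the other two strata have no events. Independently of any assumed rate, zero events in the all-age column excludes rates above 1.6%, while zero events in one stratum excludes only rates above 4.8%. These figures assume the planned 75 per cell. The conclusion rests on reading *study group* as Table S2 defines it. Confidence is moderate, because the sample-size text uses *group* differently and the sponsor may have intended age tables.

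**What to change.** In SAP 5.1.3.2.2, replace both statements that summaries are by study group with: *by study group within each age stratum (10–18, 19–64 and ≥ 65 years), and by study group over all ages*.

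In SAP Table 5.1, add *by age stratum and overall* to every row: immediate unsolicited systemic AEs, extensive limb swelling, solicited injection site reactions, solicited systemic reactions, unsolicited AEs, SAEs and MAAEs. Align Protocol 12.1.2 and the synopsis, or record the change in SAP 5.7.

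The cost is more table columns. No new data are needed and the sample size does not change. SAP 5.1.3.1 tests no hypotheses, so there is no multiplicity adjustment. The drawback is lower precision in each cell; keeping the all-age column preserves the stated detection probabilities for rarer events.

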5.1.3.2.3 Immunogenicity

Descriptive statistics will include, but not be limited to:

Table 5.2: Statistical analyses for immunogenicity observational objectives

Antigen	Time and Group	Description
Tetanus and diphtheria	At D0 and D30 for all subjects in Groups 1 - 6	GMC and 95% CI (unadjusted and adjusted)
		RCDC
		Percentage of subjects with concentration ≥ 0.01 IU/mL and 95% CI
		Percentage of subjects with concentration ≥ 0.10 IU/mL and 95% CI
		Percentage of subjects with concentration ≥ 1.0 IU/mL and 95% CI
PT, FHA, PRN and FIM	At D0 and D30 for all subjects in Groups 1 - 6	GMC and 95% CI (unadjusted and adjusted)
		RCDC
		Percentage of subjects with booster response from D0 to D30 and 95% CI ()

- ***For pertussis, immunogenicity of SP0173 investigational formulations will be assessed by comparison of post-vaccination GMCs to the following:***
- In adolescents and adults:
 - booster response rates and
 - antibody GMCs
 - after a single Adacel[®] dose
- In older adults:
 - booster response rates to pre-determined criteria (must be greater than 60%)
 - antibody GMCs compared to that after 3 doses of DTaP (Daptacel[®]) vaccine given to infants in the historical Sweden I efficacy trial (for FHA, PRN and FIM) or after 4 doses of Daptacel vaccine given to per-protocol subjects in Sanofi Pasteur Study M5A10 (for PT)

For sera obtained after vaccination, in addition to unadjusted GMCs, GMCs will be computed using analysis of covariance to adjust for baseline disparities, i.e., through an ANCOVA model using the pre-vaccination concentration as a covariate for adjustment in order to account for the variability linked to the baseline concentration and to provide a "change from baseline" analysis.

Note booster response rates partially adjust for individual and population differences in pre-vaccination antibody concentrations, so no further baseline adjustment is necessary.

For *diphtheria and tetanus*, immunogenicity of the investigational formulations in each of the age groups will be assessed by comparison to booster response rates, seroprotection rates and post-vaccination GMCs after a single Adacel[®] dose.

5.1.4 Complementary Output

Additional analyses for subjects aged 65 to 74 years and subjects aged ≥ 75 years may be provided in Appendix 15 of the CSR.

5.2 Analysis Sets

Three analysis sets will be used: The Per-Protocol Analysis Set, the Full Analysis Set, and the Safety Analysis Set.

5.2.1 Per-Protocol Analysis Set

The per-protocol analysis set (PPAS) is a subset of the FAS. The subjects presenting with at least one of the following relevant protocol deviations will be excluded from the PPAS:

- Subject did not meet all protocol-specified inclusion criteria or met at least one of the protocol-specified exclusion criteria
- Subject did not receive vaccine
- Subject received a vaccine other than the one that he/she was randomized to receive
- Preparation and/or administration of vaccine was not done as per-protocol
- Subject did not receive vaccine in the proper time window (this is a standard criterion that refers to the interval between vaccines, but does not apply in this study, as there is only one vaccine, unless one applies it to being assigned to the correct stratum).
- Subject did not provide post-dose serology sample in the proper time window or a post-dose serology sample was not drawn
- Subject received a protocol-prohibited medication
- Subject's post-dose serology sample did not produce a valid test result for all antigens, i.e., a subject would have to have no post-dose antigens with a valid test result to be excluded from PPAS for this criterion.

5.2.2 Full Analysis Set

The full analysis set (FAS) is defined as the subset of randomized subjects who received at least one dose of the study vaccine. Subjects will be analyzed according to the vaccine to which they were randomized. If a subject receives only vaccines received out of the protocol design, his data will be excluded from the analysis (and listed separately).

